4.2.1 Inclusion Criteria

1) Signed Written Informed Consent

- a) Freely given informed consent must be obtained prior to clinical trial participation, including informed consent for any screening procedures conducted to establish subject eligibility for the trial. Minor's parents or legally acceptable representatives must give fully informed written consent. Assent should be obtained when the minor is judged to be of an age of reason (see [Appendix 1](#));

2) Target Population

- a) History of CHB infection defined as HBsAg-positive at the Screening visit and on at least one other occasion ≥ 24 weeks prior to screening;
- b) Detectable HBeAg AND no detectable anti-HBe antibodies at screening and at least once ≥ 4 weeks prior to screening;
- c) Serum ALT 1.5 to $< 10 \times$ ULN at screening and at least on one other occasion within 8 to 24 weeks prior to screening;
- d) HBV DNA by PCR $\geq 10^5$ copies/mL at screening and evidence of the presence of HBV DNA at least once ≥ 4 weeks prior to screening;

3) Age and Sex

- a) Male and females, 2 to < 18 years of age.

Women of childbearing potential (WOCBP) must be using an adequate method of contraception to avoid pregnancy throughout the study and for up to 6 weeks after the last dose of investigational product in such a manner that the risk of pregnancy is minimized.

WOCBP include any female who has experienced menarche and who has not undergone successful surgical sterilization (hysterectomy, bilateral tubal ligation,

or bilateral oophorectomy) or is not postmenopausal. Post menopause is defined as:

- Amenorrhea \geq 12 consecutive months without another cause or
- For women with irregular menstrual periods and on hormone replacement therapy (HRT), a documented serum follicle stimulating hormone (FSH) level $>$ 35 mIU/mL

Women who are using oral contraceptives, other hormonal contraceptives (vaginal products, skin patches, or implanted or injectable products), or mechanical products such as an intrauterine device or barrier methods (diaphragm, condoms, spermicides) to prevent pregnancy, or are practicing abstinence or where their partner is sterile (eg, vasectomy) should be considered to be of childbearing potential.

WOCBP must have a negative serum or urine pregnancy test (minimum sensitivity 25 IU/L or equivalent units of HCG) at screening AND within 72 hours prior to the start of investigational product.

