8.4.2 Safety Analyses

Serious adverse events and deaths will be reported for enrolled subjects regardless of treatment status. Discontinuations due to adverse events will be summarized. Other safety evaluations will be reported for Treated Subjects during the following study periods: on-study treatment (from the start of dosing until end of dosing plus 5 days), and off-treatment follow-up (from the end of dosing plus 6 days until the start of alternative anti-HBV therapy or the end of follow-up, whichever is earlier). Adverse events will be summarized by severity and relationship to study medication. Laboratory abnormalities will be summarized by modified Division of AIDS (DAIDS) or World Health Organization (WHO) grades (when pediatric specific DAIDS grading are not available). The events of HBV disease progression will be tabulated.

In addition, subgroup analysis by age group will be performed for adverse events, serious adverse events, discontinuations due to adverse events, HBV disease progression and laboratory abnormalities.

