PUBLISH DATE: DECEMBER, 2004**

LABORATORY				
PARAMETER	GRADE 1 MILD	GRADE 2 MODERATE	GRADE 3 SEVERE	GRADE 4 POTENTIALLY LIFE-THREATENING
Infant[†], 22 – 35 days (HIV POSITIVE OR NEGATIVE)	9.5 – 10.5 g/dL 1.47 – 1.63 mmol/L	8.0 – 9.4 g/dL 1.24 – 1.46 mmol/L	7.0 – 7.9 g/dL 1.09 – 1.23 mmol/L	< 7.00 g/dL < 1.09 mmol/L
Infant[†], 1 – 21 days (HIV POSITIVE OR NEGATIVE)	12.0 – 13.0 g/dL 1.86 – 2.02 mmol/L	10.0 – 11.9 g/dL 1.55 – 1.85 mmol/L	9.0 – 9.9 g/dL 1.40 – 1.54 mmol/L	< 9.0 g/dL < 1.40 mmol/L
International Normalized Ratio of prothrombin time (INR)	1.1 – 1.5 x ULN	1.6 – 2.0 x ULN	2.1 – 3.0 x ULN	> 3.0 x ULN
Methemoglobin	5.0 – 10.0%	10.1 – 15.0%	15.1 – 20.0%	> 20.0%
Prothrombin Time (PT)	1.1 – 1.25 x ULN	1.26 – 1.50 x ULN	1.51 – 3.00 x ULN	> 3.00 x ULN
Partial Thromboplastin Time (PTT)	1.1 – 1.66 x ULN	1.67 – 2.33 x ULN	2.34 – 3.00 x ULN	> 3.00 x ULN
Platelets, decreased	100,000 – 124,999/mm ³ 100,000 x 10⁹ – 124,999 x 10⁹/L	50,000 – 99,999/mm ³ 50,000 x 10⁹ – 99,999 x 10⁹/L	25,000 – 49,999/mm ³ 25,000 x 10⁹ – 49,999 x 10⁹/L	< 25,000/mm ³ < 25,000 x 10⁹/L
WBC, decreased	2,000 – 2,500/mm ³ 2,000 x 10⁹ – 2,500 x 10⁹/L	1,500 – 1,999/mm ³ 1,500 x 10⁹ – 1,999 x 10⁹/L	1,000 – 1,499/mm ³ 1,000 x 10⁹ – 1,499 x 10⁹/L	< 1,000/mm ³ < 1,000 x 10⁹/L
CHEMISTRIES Standard International Units are listed in italics				
Acidosis	NA	pH < normal, but ≥ 7.3	pH < 7.3 without life- threatening consequences	pH < 7.3 with life- threatening consequences
Albumin, serum, low	3.0 g/dL – < LLN 30 g/L – < LLN	2.0 – 2.9 g/dL 20 – 29 g/L	< 2.0 g/dL < 20 g/L	NA
Alkaline Phosphatase	1.25 – 2.5 x ULN [†]	2.6 – 5.0 x ULN [†]	5.1 – 10.0 x ULN [†]	> 10.0 x ULN [†]
Alkalosis	NA	pH > normal, but ≤ 7.5	pH > 7.5 without life- threatening consequences	pH > 7.5 with life- threatening consequences
ALT (SGPT)	1.25 – 2.5 x ULN	2.6 – 5.0 x ULN	5.1 – 10.0 x ULN	> 10.0 x ULN
AST (SGOT)	1.25 – 2.5 x ULN	2.6 – 5.0 x ULN	5.1 – 10.0 x ULN	> 10.0 x ULN
Bicarbonate, serum, low	16.0 mEq/L – < LLN 16.0 mmol/L – < LLN	11.0 – 15.9 mEq/L 11.0 – 15.9 mmol/L	8.0 – 10.9 mEq/L 8.0 – 10.9 mmol/L	< 8.0 mEq/L < 8.0 mmol/L
Bilirubin (Total)				
Adult and Pediatric > 14 days	1.1 – 1.5 x ULN	1.6 – 2.5 x ULN	2.6 – 5.0 x ULN	> 5.0 x ULN

[†] Values are for term infants.

[†] Use age and sex appropriate values (e.g., bilirubin), including preterm infants.

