**DIVISION OF AIDS TABLE FOR GRADING THE SEVERITY OF
ADULT AND PEDIATRIC ADVERSE EVENTS
PUBLISH DATE: DECEMBER, 2004**

LABORATORY				
PARAMETER	GRADE 1 MILD	GRADE 2 MODERATE	GRADE 3 SEVERE	GRADE 4 POTENTIALLY LIFE-THREATENING
Infant [†] , ≤ 14 days (non-hemolytic)	NA	20.0 – 25.0 mg/dL 342 – 428 μmol/L	25.1 – 30.0 mg/dL 429 – 513 μmol/L	> 30.0 mg/dL > 513.0 μmol/L
Infant [†] , ≤ 14 days (hemolytic)	NA	NA	20.0 – 25.0 mg/dL 342 – 428 μmol/L	> 25.0 mg/dL > 428 μmol/L
Calcium, serum, high (corrected for albumin)				
Adult and Pediatric ≥ 7 days	10.6 – 11.5 mg/dL 2.65 – 2.88 mmol/L	11.6 – 12.5 mg/dL 2.89 – 3.13 mmol/L	12.6 – 13.5 mg/dL 3.14 – 3.38 mmol/L	> 13.5 mg/dL > 3.38 mmol/L
Infant [†] , < 7 days	11.5 – 12.4 mg/dL 2.88 – 3.10 mmol/L	12.5 – 12.9 mg/dL 3.11 – 3.23 mmol/L	13.0 – 13.5 mg/dL 3.245 – 3.38 mmol/L	> 13.5 mg/dL > 3.38 mmol/L
Calcium, serum, low (corrected for albumin)				
Adult and Pediatric ≥ 7 days	7.8 – 8.4 mg/dL 1.95 – 2.10 mmol/L	7.0 – 7.7 mg/dL 1.75 – 1.94 mmol/L	6.1 – 6.9 mg/dL 1.53 – 1.74 mmol/L	< 6.1 mg/dL < 1.53 mmol/L
Infant [†] , < 7 days	6.5 – 7.5 mg/dL 1.63 – 1.88 mmol/L	6.0 – 6.4 mg/dL 1.50 – 1.62 mmol/L	5.50 – 5.90 mg/dL 1.38 – 1.51 mmol/L	< 5.50 mg/dL < 1.38 mmol/L
Cardiac troponin I (cTnI)	NA	NA	NA	Levels consistent with myocardial infarction or unstable angina as defined by the manufacturer
Cardiac troponin T (cTnT)	NA	NA	NA	≥ 0.20 ng/mL OR Levels consistent with myocardial infarction or unstable angina as defined by the manufacturer
Cholesterol (fasting)				
Adult ≥ 18 years	200 – 239 mg/dL 5.18 – 6.19 mmol/L	240 – 300 mg/dL 6.20 – 7.77 mmol/L	> 300 mg/dL > 7.77 mmol/L	NA
Pediatric < 18 years	170 – 199 mg/dL 4.40 – 5.15 mmol/L	200 – 300 mg/dL 5.16 – 7.77 mmol/L	> 300 mg/dL > 7.77 mmol/L	NA
Creatine Kinase	3.0 – 5.9 x ULN [‡]	6.0 – 9.9 x ULN [‡]	10.0 – 19.9 x ULN [‡]	≥ 20.0 x ULN [‡]
Creatinine	1.1 – 1.3 x ULN [‡]	1.4 – 1.8 x ULN [‡]	1.9 – 3.4 x ULN [‡]	≥ 3.5 x ULN [‡]
Glucose, serum, high				
Nonfasting	116 – 160 mg/dL 6.44 – 8.88 mmol/L	161 – 250 mg/dL 8.89 – 13.88 mmol/L	251 – 500 mg/dL 13.89 – 27.75 mmol/L	> 500 mg/dL > 27.75 mmol/L
Fasting	110 – 125 mg/dL 6.11 – 6.94 mmol/L	126 – 250 mg/dL 6.95 – 13.88 mmol/L	251 – 500 mg/dL 13.89 – 27.75 mmol/L	> 500 mg/dL > 27.75 mmol/L

^{*} Values are for term infants.

[‡] Use age and sex appropriate values (e.g., bilirubin), including preterm infants.

**DIVISION OF AIDS TABLE FOR GRADING THE SEVERITY OF
ADULT AND PEDIATRIC ADVERSE EVENTS
PUBLISH DATE: DECEMBER, 2004**

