## 6 STUDY PERIODS, TREATMENT REGIMENS AND POPULATIONS FOR ANALYSES

### 6.1 Study Periods

Study periods for efficacy and safety analyses are defined as follows:

- **Pre-treatment period** begins at the first visit until initiation of study therapy.
- **On-treatment period** begins after the first day of study therapy and ends at the last dose of study therapy plus 5 days.
- **ETV treatment period** begins after the first day of active ETV and ends at the last dose of active ETV plus 5 days.
- **Off-treatment follow-up period** begins on the last dose of study therapy plus 6 days and ends at the start of alternative anti-HBV therapy minus 1 day.
- **Long-term follow-up period** begins on the last dose of study therapy plus 6 days until the end of the study.
- **Alternative ETV follow-up period** begins on the later of the last dose of study therapy plus 6 days and the start of alternative ETV therapy, until the end of the study.

Note that rescue open-label ETV is considered alternative anti-HBV therapy. See [Section 8.9](#) for additional conventions.

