#### **7.6.6.1 Laboratory Abnormalities**

For each laboratory test, laboratory abnormalities by toxicity grade (Grade 1 - 4; Grade 3 - 4) on treatment are summarized by treatment regimen and baseline status (all, normal, abnormal, not reported) for the following 3 cohorts:

- Through Week 48 on blinded therapy for treated subjects
- After Week 48 on blinded therapy or on open-label ETV through Week 96 for the Year 2 Safety Cohort
- On ETV treatment for All ETV Safety Cohort

Laboratory tests include:

- Hematology: hemoglobin, platelets, international normalized ratio (INR), white blood cell count (WBC) and neutrophils + bands (absolute)
- Liver function tests: alanine aminotransferase (ALT), aspartate aminotransferase (AST), total bilirubin and albumin
- Pancreatic enzymes: lipase (colorimetric or turbidimetric assay)
- Renal function tests: creatinine and BUN/urea (BUN or urea)
- Electrolytes (low and high): chloride, potassium and sodium.

Toxicity grades are based on DAIDS, unless specified otherwise (see Protocol Appendix 2). BUN/urea and chloride are graded with modified WHO criteria.

Treatment emergent laboratory abnormalities by toxicity grade (increased to Grades 1, 2, 3 and 4) are also summarized analogously by treatment regimen and baseline status for the 3 cohorts. On-treatment emergent abnormalities are those with a higher toxicity grade than the baseline toxicity grade (including not reported baseline).

In addition, the following select laboratory elevations and abnormalities on treatment are summarized by treatment regimen for the 3 cohorts:

- Any Grade 3 - 4 laboratory abnormality (see previous list of tests)
- Liver function elevations  $> 2$  and  $> 3$  x baseline (ALT, AST, total bilirubin)
- Liver function elevations  $> 2$  x baseline and Grade 4 (ALT, AST and total bilirubin; includes ALT flares, defined as ALT  $> 2$  x baseline and  $> 10$  x ULN)
- Simultaneous ALT and total bilirubin elevations (ALT  $> 2$  x baseline, total bilirubin  $> 2$  x baseline and  $> 2$  x ULN; ie, those occurring on the same collection day).

- Albumin < 2.5 g/dL
- Lipase elevations > 3 x baseline
- Confirmed creatinine elevations  $\geq 0.3$  and  $\geq 0.5$  mg/mL from baseline (2 sequential measurement or last measurement meeting the elevation criteria)
- Glucose categories (< 50,  $\geq 200$  mg/dL) regardless of fasting status.

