### Eligibility Deviations

Eligibility deviations (ie, protocol deviations of entry criteria) are listed below.

- Inclusion 2b: HBeAg negative or missing, or HBeAb positive or missing at screening
- Inclusion 2c: ALT < 1.5 x ULN or  $\geq 10 \times$  ULN or missing at screening
- Inclusion 2d: HBV DNA <  $10^5$  c/mL or missing at screening
- Inclusion 3a: Age < 2 or  $\geq 18$  years
- Exclusion 1d: Women with positive pregnancy test at screening
- Exclusion 2a: Positive test for HIV, HCV or HDV at screening.
  - HCV positive is defined as both HCV antibody positive and detectable HCV RNA.
  - HIV positive is defined as having a positive result for HIV-1 and HIV-2 screen and either HIV-1 confirmation or the HIV-2 confirmation immunoblot.
- Exclusion 4a: Hemoglobin < 10.0 g/dL or missing at screening
- Exclusion 4b: Platelets count <  $70,000/\text{mm}^3$  or missing at screening
- Exclusion 4c: Glomerular filtration rate < 50 mL/min/1.73 m^2 or missing at screening. This is estimated using Schwartz formula.
- Exclusion 4d: Total bilirubin > 2.5 mg/dL (> 42.75  $\mu\text{mol/L}$ ) or missing at screening
- Exclusion 4e: INR > 1.5 or missing at screening
- Exclusion 4f: Albumin < 3 g/dL (< 30 g/L) or missing at screening
- Exclusion 4 g: Alpha fetoprotein  $\geq 50$  ng/mL or missing at screening
- Exclusion 6a: Prior therapy  $\geq 12$  weeks with any anti-HBV nucleoside or nucleotide. This includes, but is not limited to adefovir, tenofovir, famciclovir, clevudine, lamivudine, telbivudine or emtricitabine (#)
- Exclusion 6b: Prior therapy with interferon alpha, thymosin alpha or any anti-HBV nucleos[t]ide antiviral agent within 24 weeks of screening (#)
- Exclusion 6c: Prior ETV

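### The pooled on-treatment Grade 3-4 laboratory row in SAP 7.6.6.1 counts ALT that was already Grade 3 at entry, so it mixes entry disease with on-treatment harm

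*Protocol*

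**What the plan says.** - **Entry.** Protocol 4.2.1, criterion 2c, requires "Serum ALT 1.5 to $< 10 \times$ ULN at screening". SAP Appendix 1 programs the matching deviation, beginning "Inclusion 2c: ALT < 1.5 x ULN or". No entry limit is set for AST.
- **Grades.** Protocol Appendix 2 gives ALT Grades 1, 2 and 3 as "ALT (SGPT) 1.25 – 2.5 x ULN 2.6 – 5.0 x ULN 5.1 – 10.0 x ULN", with Grade 4 above 10.0 x ULN. AST has the same limits.
- **The pooled row.** The select list in SAP 7.6.6.1 includes "Any Grade 3 - 4 laboratory abnormality (see previous list of tests". The list it points to contains "Liver function tests: alanine aminotransferase (ALT), aspartate aminotransferase (AST), total bilirubin and albumin". Nothing in the row refers to baseline.
- **What counts as on treatment.** Under SAP 6.1 the period "begins after the first day of study therapy and ends at the last dose of study therapy plus 5 days". SAP 7.6.6.1 reports, for each test, the value with the highest grade in the period.
- **What else the section plans.** For the same three on-treatment cohorts there are per-test grade tables by baseline status, per-test treatment-emergent tables (grade above the baseline grade), and several select rows defined against baseline. The follow-up version of the select list is stated relative to the end-of-dosing value.
- **Subgroups.** SAP 7.6.8 carries the per-test grade tables and the select list into subgroup summaries through Week 48. It does not list the treatment-emergent tables.

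**The concern.** A pooled row of severe laboratory abnormalities is naturally read as a per-child count of laboratory harm. Here raised ALT is an entry requirement, and the permitted range overlaps Grade 3. A child who enters at 8 x ULN and is at 6 x ULN at Week 4 has improved, yet is counted.

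The two arms need not carry this over equally. ALT normalization is a key secondary endpoint (SAP 7.5.2.2), tested as ETV against placebo. If ETV works on that endpoint, Grade 3 ALT from entry should persist less often on ETV. The pooled row would then shift in ETV's favour for a reason unrelated to toxicity, and could offset an ETV excess in other tests within that row.

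**Working it through.** The documents give no laboratory event rates, so there is no figure of the plan's own to reproduce here. The sample size of 123 does not enter.

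**Step 1: can a child enter at Grade 3?** Entry allows 1.5 to below 10 x ULN; Grade 3 is 5.1 to 10.0 x ULN. The overlap is 5.1 to below 10 x ULN, so yes. By contrast, the entry limits for haemoglobin (10.0 g/dL), platelets (70,000/mm³) and albumin (3.0 g/dL) all lie above the corresponding Grade 3 ranges in Appendix 2 (7.0-8.9 g/dL, 25,000-49,999/mm³, below 2.0 g/dL).

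**Step 2: does that child count?** Not from the baseline value, because the period starts after Day 1. A later value must itself be Grade 3 or 4. Visits fall at Weeks 4, 8, 12 and then every 12 weeks, and the worst grade is used, so one Week 4 value still at Grade 3 is enough. The emergent rule would not count that child; the pooled row does.

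**Step 3: size, as an illustration.** All rates are assumptions:
- q = share entering at ALT Grade 3: 10%, 20%, 30%
- r = share of these with Grade 3 ALT at some on-treatment visit: 60-80% on ETV, 90-100% on placebo
- o = Grade 3-4 in tests other than ALT and AST: 10% on ETV, 5% on placebo (true difference +5 points)
- ALT and other tests independent; new ALT worsening and separate AST events ignored

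Pooled row = 1 − (1 − q·r)(1 − o).

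| q | ETV, r = 0.6 | ETV, r = 0.8 | Placebo, r = 0.9 | Placebo, r = 1.0 |
|---|---|---|---|---|
| 10% | 1 − 0.94×0.90 = 15.40% | 1 − 0.92×0.90 = 17.20% | 1 − 0.91×0.95 = 13.55% | 1 − 0.90×0.95 = 14.50% |
| 20% | 1 − 0.88×0.90 = 20.80% | 1 − 0.84×0.90 = 24.40% | 1 − 0.82×0.95 = 22.10% | 1 − 0.80×0.95 = 24.00% |
| 30% | 1 − 0.82×0.90 = 26.20% | 1 − 0.76×0.90 = 31.60% | 1 − 0.73×0.95 = 30.65% | 1 − 0.70×0.95 = 33.50% |

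Difference ETV − placebo, lowest to highest over all four pairings:
- q = 10%: 15.40 − 14.50 = +0.9 to 17.20 − 13.55 = +3.65 (+3.7)
- q = 20%: 20.80 − 24.00 = −3.2 to 24.40 − 22.10 = +2.3
- q = 30%: 26.20 − 33.50 = −7.3 to 31.60 − 30.65 = +0.95

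**Step 4: equal persistence.** If r is the same in both arms, the difference is (1 − q·r) × 5 points. At q = 20%, r = 0.8 this is 0.84 × 5 = +4.2. The row is then diluted but never reversed.

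**Step 5: is an emergent-only row enough?** Suppose new ALT worsening to Grade 3-4 occurs in 5% on ETV and 15% on placebo (again assumed). An emergent row shows 1 − 0.95×0.90 = 14.50% against 1 − 0.85×0.95 = 19.25%, a difference of −4.75 points. These are genuine events, but the row still does not show the other toxicities. A row without ALT and AST shows the +5.

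**The case against.** The strongest reply is that the SAP already answers the main worry. Each test is tabulated by grade and again as treatment-emergent for the same three cohorts, and the same select list has baseline-relative rows for ALT, AST, bilirubin, lipase and creatinine. The pooled row is one descriptive line with no test or decision rule. All of that stands.

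It does not dispose of the point. Single-test tables cannot be added into a per-child count, and no pooled emergent row is planned. The baseline-status split (normal, abnormal, not reported) cannot isolate Grade 3 entrants, since ALT above ULN is required at screening. SAP 7.6.8 uses the select list without the emergent tables.

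Four stronger readings might be inferred, and the documents do not support them:
- *An ETV toxicity could be hidden from the report.* An excess in lipase, haematology or bilirubin would appear in its own per-test and emergent tables.
- *The row will reverse sign.* That needs ALT to fall more on ETV. Even at 30% Grade 3 entry, the assumed ranges reach +0.95.
- *Every eligible child starts treatment with at least Grade 1 ALT.* The criterion applies at screening, up to 6 weeks before randomization. SAP 8.5 takes baseline as the last value up to first dose.
- *Severe glucose values are lost because glucose is not in the graded list.* The planned categories, below 50 and at least 200 mg/dL, contain every Grade 3-4 value in Appendix 2: 30-39 and below 30 mg/dL on the low side, "251 – 500 mg/dL 13.89 – 27.75 mmol/L" and above 500 mg/dL on the high side. Protocol 8.4.2 says "Laboratory abnormalities will be summarized by modified Division of AIDS (DAIDS) or World Health Organization (WHO) grades", which does not promise that every analyte is graded.

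**Conclusion.** The point holds for the pooled on-treatment row and its reuse in the SAP 7.6.8 subgroups, and no further. That the row lacks a baseline condition, and that Grade 3 ALT is permitted at entry, follows from the text alone. Dilution follows if some entrants stay at Grade 3 on treatment; a shift in ETV's favour requires in addition that fewer of them do so on ETV than on placebo. The size rests wholly on assumed rates: a true +5 points could appear as anything from +3.7 to −7.3 over 10-30% Grade 3 entry. The primary result, alpha and power are untouched. This is a cheap improvement to how pooled laboratory safety is presented.

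**What to change.** In SAP 7.6.6.1, add two rows to the select list:
1. *Any treatment-emergent Grade 3-4 laboratory abnormality*, using the section's existing rule (grade above the baseline grade for that test, with ETV baseline during open-label ETV for placebo subjects).
2. *Any Grade 3-4 laboratory abnormality excluding ALT and AST*. This is needed because the first row would still include ALT flares on placebo.

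Carry both into the SAP 7.6.8 subgroup summaries. The existing row can stay. No change to glucose reporting is needed. The cost is SAP wording and two more table rows, with no new data.

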## 2 STUDY DESCRIPTION

### 2.1 Study Design

This is a comparative, randomized, double-blinded, placebo-control, multicenter study, assessing the efficacy and safety of ETV in pediatric subjects with chronic HBV infection who are HBeAg-positive and nucleos[t]ide naive (< 12 weeks of prior therapy with any nucleos[t]ide antiviral agent with activity against hepatitis B virus). Chronic HBV-infected children and adolescents from 2 to < 18 years of age will be enrolled. Approximately 180 subjects will be randomized 2:1 to ETV or placebo (PBO) for a maximum of 96 weeks of blinded therapy, with the primary endpoint at Week 48 for the first 123 randomized subjects (the Primary Cohort). The randomization will be stratified by age group ( $\geq 2$  to  $\leq 6$ ,  $> 6$  to  $\leq 12$ ,  $> 12$  to  $< 18$  years). To ensure adequate representation, the target enrollment will be 30 subjects for each age group, with a minimum requirement of 18 subjects. At Week 52, an assessment of HBeAg seroconversion shall be performed based on Week 48 serology results. At the Week 52 assessment, all subjects who achieve HBeAg seroconversion will remain on blinded therapy through Week 96; subjects without HBeAg seroconversion will be switched to open-label ETV. Thereafter, assessment of HBeAg seroconversion shall be conducted at study Weeks 100 and 148 during the open label treatment. Study subjects who achieve HBeAg seroconversion during open label ETV at the respective assessment time points shall receive up to an additional 48 weeks of study treatment for consolidation (extended treatment to strengthen study drug effects). Open-label ETV may therefore be continued up to Week 144 in ETV randomized subjects and Week 192 for placebo randomized subjects. All randomized study subjects who do not achieve HBeAg seroconversion will receive a maximum of 96 weeks of study ETV therapy.

After completing the blinded treatment or the open-label phase, all subjects will be followed in an observational long-term follow up phase until they complete a total of 5 years of study participation from the start of blinded treatment.

The total duration of the study will be 264 weeks (5 years); the end of the study is defined as the date of the last follow-up visit. Study visits will occur at screening, Baseline, Weeks 4, 8, 12, and

then every 12 weeks during study treatment. Additional ‘On Treatment’ visits to modify or discontinue study drug based on HBeAg assessments will occur at Weeks 52, 100, and 148, if needed. At selected sites, a subset of up to 9 treated subjects in each age cohort will have 4 plasma specimens collected for semi-intense pharmacokinetic assessments during a single visit between study Day 14 and Week 4. Once in the observational long-term follow-up phase, study visits will occur at Weeks 6, 12, and then every 12 weeks until completion of a total of 264 weeks of “on-study follow-up”.

